6.7. Dose Titration and Insulin Lispro Re-introduction

The albiglutide dose in this study will start at 30 mg weekly and be titrated to 50 mg weekly at Week 4.

Both treatment arms will follow the same insulin glargine titration algorithm during the Standardization and Treatment Periods (see Table 3 of the Protocol).

Both treatment arms will follow the same insulin lispro titration algorithm during the standardization period. At randomization, the start of the treatment period, the insulin lispro titration algorithm will be individualized for each treatment arm (see Table 4 of the protocol).

Insulin lispro may be re-introduced after Week 8 for subjects in the albiglutide treatment group. The number of subjects for whom insulin lispro was re-introduced will be summarized. For these subjects, the re-introduced insulin lispro will be characterized in terms of the number of injections and the total dose over time. The dosing guidance for albiglutide, insulin lispro, insulin glargine, and metformin treatment can be found in Table 2 of the Protocol.

Individual dose titration information and insulin lispro re-introduction will be listed for the safety population.

For lispro re-introduction through Week 26, it will include lispro re-introduced up to Week 25 and not include lispro prescribed at Week 26. This is due to that the last albiglutide injection is given at Week 25 for subjects in albiglutide arm and at Week 26 lispro may be prescribed as per standard of care.

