8.1.2.4. Prescribed Total Daily Insulin Doses and Total Number of Weekly Insulin Injections

Prescribed total daily insulin doses at Baseline, Week 4, 5, 10, 18 and 26 will be assessed from several aspects:

- Total daily insulin dose (IU)
- Body weight adjusted total daily insulin dose (IU/kg)
- Total daily basal insulin (insulin glargine) dose (IU)
- Body weight adjusted total daily basal insulin (insulin glargine) dose
- Total daily bolus insulin (insulin lispro) dose (IU)
- Body weight adjusted total daily bolus insulin (insulin lispro) dose

The absolute value in each of the above variables by visit will be analyzed using an MMRM model similar to Model 2 where the specific insulin dose replaces weight (Section 8.1.2.3). The prescribed total daily insulin doses will be summarized descriptively and presented graphically by treatment group. The least squares means (and standard errors) of the prescribed total daily insulin doses will be plotted by treatment group.

In addition, total number of weekly insulin injections (7 days) to achieve glycemic control at Baseline, Week 4, 5, 10, 18 and 26 will also be assessed and summarized using descriptive statistics; the value for this analysis is derived based on the number of prescribed insulin injections as follows:

- Albiglutide: 1 injection per week
- Insulin Glargine: 1 injection per day (7 injections per week)
- Insulin Lispro: 3 injections per day (21 injections per week)

For subjects who was randomized to the albiglutide arm and required re-introduction of insulin lispro, the number of injections for insulin lispro should be based on data collected in the Surveillance eCRF page. These subjects could have once-daily, twice-daily or three times daily insulin lispro injections.

Definitions for insulin dose and number of injections at Week 26 for albiglutide arm:

- Both glargine and lispro dose at Week 26 will be defined operationally as the prescribed dose at Week 25.
- For lispro number of injections at Week 26 will be defined operationally as the prescribed number of injections at Week 25. For glargine number of injections at Week 26 will be considered 1 per day.

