11.3.4. Analysis Visit Windows

Table - Analysis Visit Windows

Scheduled Visit	Target Study Day of Visit	Slotting Intervals
Week -6	-42	Visit = " SCREENING"
Week -4	-28	Visit = " STANDARDIZATION 1"
Week -1	-7	Visit = " STANDARDIZATION 4"
Baseline (Week 0)	1	Visit = " BASELINE"
Week 4	29	2 to 32 days
Week 5	36	33 to 53 days
Week 10	71	54 to 99 days
Week 18	127	100 to 155 days
Week 26 (End of Treatment Visit)*	183	Albiglutide arm: 156 to (last dose date + 25 days) Lispro arm: 156 to last dose date
Week 30**	211	For subjects completed study Albiglutide arm: >Last dose date + 25 days Lispro arm: >Last dose date
4 Week Follow-up Visit**	Last dose date + 35 days***	For subjects didn't complete study Albiglutide arm: >Last dose date + 25 days Lispro arm: >Last dose date

* Week 26 is the end of treatment visit for those subjects completing the study per-protocol. For subjects who withdraw early from active treatment, the end of treatment visit will be assigned to an analysis visit based on the visit slotting algorithm using study day and therapy phase.

** Week 30 is the 4 week post-treatment follow-up visit for those subjects completing the study per-protocol. The 4 Week Follow-up Visit is the 4 week post-treatment follow-up visit for those subjects who withdraw early from active treatment. Both visits will be assigned based on the visit slotting algorithm using therapy phase.

*** The target study day for the 4 Week Follow-up Visit for subjects who withdraw early from active treatment is set to be 5 weeks (35 days) after last dose to correspond with the timing of the 4 week post-treatment follow-up for subjects completing the study per-protocol (where last dose is at Week 25 and the follow-up visit is at Week 30).

For parameters which were not scheduled to be collected at all visits, the all-inclusive visit intervals defined for all visits (that is, the visit window table above) will still be used to slot records. However, if a value is slotted to a visit unscheduled for a parameter, it will not be summarized (and not be included in the efficacy datasets) but will be included in data listings.

For analyses on the prescribed insulin dose, the total number of weekly insulin injections and SMBG profile, visit and visit dates recorded on the eCRF are used for analysis because a specific visit date is needed to calculate the analysis values.

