11.4. Appendix 4: Treatment Periods

For classifying AEs (including hypoglycemic events), the therapy periods will be defined as:

- **Pre-therapy:** The onset date of the AE is before the start date of randomized study medication. If the onset date of the AE is on the start date of randomized study medication, the AE will be considered as on-therapy.
- **On-therapy:** The onset date of the AE is on or after the start date of randomized study medication, and within last dose date plus 25 days in the albiglutide arm or within the last dose date in the lispro arm.
- **Post-therapy:** The onset date of the AE is more than 25 days after the last dose date in the albiglutide arm or after the last dose date in the lispro arm.

For immunogenicity data and other safety parameters that are assessed prior to administration of randomized study medication on dosing days, the therapy periods will be defined as:

- **Pre-therapy:** The assessment date is on or before the start date of randomized study medication.
- **On-therapy:** The assessment date is after the start date of randomized study medication, and within last dose date plus 25 days in the albiglutide arm or within the last dose date in the lispro arm.
- **Post-therapy:** The assessment date is more than 25 days after the last dose date in the albiglutide arm or after the last dose date in the lispro arm.

For an AE with an incomplete start date where the year and month are present while the day is missing, or where the year is present while both month and day are missing, the date is imputed in a dynamic way consistent with the partial date information so that the resulting AE therapy period assignment based on the imputed date is the most conservative possible, where the order from the most to the least conservative is: on-therapy phase > post-therapy phase > pre-therapy. Note that if the AE stop date is present, the imputed start date will always be on or prior to the stop date.

For the subjects in the insulin lispro + insulin glargine arm, the first drug dispense date recorded on eCRF after randomization is considered the starting date of treatment period. For the last dose date, it will be derived based on the last visit date. The last dose date will be Week 30 follow-up visit date for subject who completed the study, or the 4-week follow-up visit/end of study visit date for subjects who withdrew early.

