11.10. Appendix 10: Multiple Comparisons & Multiplicity

A closed testing strategy will be implemented for the multiple inferential tests among the primary and key secondary endpoints to preserve overall family-wise Type I error rate of 0.05. The strategy involves pre-specification of test order [Koch, 1996].

The first test to be conducted is the primary efficacy analysis of HbA_{1c} change from Baseline at Week 26 on treatment comparison of albiglutide versus insulin lispro using non-inferiority testing. The comparison will be evaluated inferentially at the 1-sided 0.025 criterion significance level. If the non-inferiority of albiglutide is established, testing of superiority for the key secondary endpoints and the primary endpoint will proceed sequentially in a step-down manner at a 2-sided significance level of 0.05 in the following order:

- 1) Change from Baseline in body weight at Week 26
- 2) Prescribed total daily insulin dose at Week 26
- 3) Change from baseline in HbA_{1c} at Week 26

If a test for higher order endpoints above does not reach statistical significance, the results of statistical tests for lower order endpoints will not be interpreted.

Note that for one of the key secondary endpoints listed in the protocol, proportion of subjects treated with once-weekly albiglutide that are able to discontinue insulin lispro at Week 4 and do not meet prespecified criteria for severe, persistent hyperglycemia through Week 26, treatment comparison is not applicable as it is only defined for the Albiglutide + Insulin Glargine arm.

This is a treat-to-target study with the primary efficacy endpoint HbA_{1c} as the measurement. By the study design of treat-to-target, change from baseline in HbA_{1c} values in both treatment groups (Albiglutide + Insulin Glargine versus Insulin Lispro + Insulin Glargine), is expected to reach the target, and thus not expected to show a significant difference. Thus, testing of superiority for change from Baseline in HbA_{1c} at Week 26 is considered lowest priority in the hierarchy of the multiple testing procedure.

Testing on other efficacy or exploratory endpoints, if applicable, will be considered exploratory and no multiplicity adjustment will be applied. Any secondary and exploratory endpoints that do not qualify for formal statistical testing will be analyzed and have results presented with confidence intervals and nominal p-values, if applicable.

The order of the testing strategy is shown in the diagram below.

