
Albiglutide + Insulin Glargine versus Insulin Lispro + Insulin Glargine

Primary Efficacy Endpoint -
HbA1c Change from Baseline at

Key Secondary Efficacy Endpoint
1 - Percentage of subjects with

Key Secondary Efficacy Endpoint
2 - Change from Baseline in body

Key Secondary Efficacy Endpoint
3 - Total daily insulin dose at

Primary Efficacy Endpoint -
HbA1c Change from Baseline at

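### The confirmatory Week 26 insulin-dose comparison takes the Week 25 prescription in the albiglutide arm but, by default, the Week 26 visit prescription in the lispro arm

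*SAP*

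**What the plan says.** SAP 8.1.2.4 plans to analyse prescribed total daily insulin dose at Baseline and Weeks 4, 5, 10, 18 and 26. It closes with a block headed "Definitions for insulin dose and number of injections at Week 26 for albiglutide arm", whose first item reads "Both glargine and lispro dose at Week 26 will be defined operationally as the prescribed dose at Week 25". No corresponding item follows for the lispro arm. The injection count for lispro is set earlier in the same section: "Insulin Lispro: 3 injections per day (21 injections per week".

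SAP 11.3.4 has a general rule for prescribed-dose analyses that does not distinguish the arms: "visit and visit dates recorded on the eCRF are used for analysis because a specific visit date is needed".

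The reason for avoiding Week 26 in the albiglutide arm appears in SAP 6.7, in the context of lispro re-introduction. The last albiglutide injection is at Week 25, and "at Week 26 lispro may be prescribed as per standard of care".

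For the lispro arm, SAP 11.4 extends treatment past Week 26: "The last dose date will be Week 30 follow-up visit date for subject who completed the study". Protocol 5.7.1 allows both insulins in that arm to be adjusted under labelling and standard of care between the Week 26 visit and follow-up.

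The endpoint is confirmatory. The step-down list in SAP 11.10 gives "2) Prescribed total daily insulin dose at Week 26" at two-sided 0.05, ahead of HbA1c superiority. The diagram in the same appendix labels it "3 - Total daily insulin dose at" (text cut off).

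**The concern.** A between-arm contrast should use one definition of its outcome. Here the albiglutide arm contributes the Week 25 prescription and the lispro arm, by default, the Week 26 one. A dose review lies between the two, so the estimated difference contains a part that reflects timing and not treatment. The same offset enters the total, basal, bolus and IU/kg dose analyses.

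The SAP 6.7 reason is a good one for using Week 25 in the albiglutide arm. It does not explain why the comparator should be read at a different point, and it does not mention glargine, which the 8.1.2.4 rule also moves. The substitution is not listed in SAP 2.1 as a change from the protocol. At stake is a clean estimate and confidence interval for a key secondary endpoint.

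**Working it through.** **Design figure, for the sample size used below.** The documents size the trial for HbA1c only. With margin 0.3, SD 1.2, true difference 0 and one-sided 0.025, the required n for 90% power is 337 per arm, as stated. At n = 337 power is 90.1% (normal) or 89.98% (noncentral t). Then 337/0.85 rounds up to 397 per arm, 794 in total. No design figure depends on this point. No SD, effect or power is given for insulin dose.

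**How far apart the readings are.**
- Target days: Week 25 = 25 × 7 + 1 = Day 176. Week 26 = Day 183 (SAP 11.3.4). Nominal gap: 7 days.
- Dose need is reviewed at the Week 25 call (Table 6) and at the Week 26 visit (Table 5). The scheduled contact before Week 25 is Week 22 (protocol 5.1.3.2).
- If the Surveillance entry is the newly set dose, the comparison is the dose set at Week 25 against the dose set at Week 26. If it is the dose in force on arrival, it is the dose set at Week 22 against the dose set at Week 25. Either way the arms differ by one scheduled review.
- The forward-looking reading has more support. SAP 2.1 describes the prescribed dose as what the investigator judges necessary, and protocol 5.1.3.4 lists doses recommended until the next contact separately from recent doses. On that reading the lispro-arm value is set for the weeks after treatment ends.

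**Limits on one review, from protocol Tables 3 and 4 (fixed-unit steps).** Largest increase: 6 + 3 × 4 = 18 IU. Largest decrease: 4 + 3 × 2 = 10 IU. Percentage reductions are an additional option in some cases.

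**Possible mean shift in the lispro arm (assumed inputs).** Shift = share of subjects changed × net change in the same direction:
- no net change: 0
- 10% × 2 IU = 0.2 IU/day
- 20% × 4 IU = 0.8 IU/day
- 30% × 6 IU = 1.8 IU/day

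**Scale of that shift.** Model 2 adjusts for baseline dose. Assume a raw SD of 30 to 50 IU and a baseline correlation r of 0.8 to 0.5. Residual SD = SD × √(1 − r²), and SE = residual SD × √(2/337).

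| Raw SD | r | Residual SD | SE | 1.8 IU in SEs |
|---|---|---|---|---|
| 30 | 0.8 | 18.0 | 1.39 | 1.30 |
| 50 | 0.5 | 43.3 | 3.34 | 0.54 |

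**Effect on the test in the least favourable case** (residual SD 43.3, 1.8 IU lost, two-sided 0.05 t test, 337 per arm):

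| True difference | Power without shift | Difference left | Power with shift |
|---|---|---|---|
| 20 IU | >0.999 | 18.2 | 0.9998 |
| 15 IU | 0.994 | 13.2 | 0.977 |
| 10 IU | 0.849 | 8.2 | 0.690 |

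**Test order in SAP 11.10.** After HbA1c noninferiority, the text list runs body weight, insulin dose, HbA1c superiority. The diagram runs a percentage-of-subjects endpoint (wording cut off) as key secondary 1, body weight as 2, insulin dose as 3, then HbA1c. The text omits an endpoint that the diagram places first, so this is more than a numbering slip.

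**The case against.** The strongest reply is that the rule is a deliberate exception with a documented basis. Albiglutide stops at Week 25, so a Week 26 prescription in that arm may belong to a different regimen. The lispro arm keeps the same two insulins, is treated as on therapy to Week 30, and has its titration loosened only once the Week 26 visit is complete. On that view each arm is read at its last on-regimen prescription, and the protocol names Week 26. This stands in part: a Week 26 reading is defensible for the lispro arm taken alone. It does not make the two readings comparable, and on the forward-looking reading the lispro-arm value is itself a post-treatment prescription.

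It is also fair that the magnitude is wholly assumed and that the power table stacks unfavourable inputs: the larger SD, the weaker correlation, and 30% of one arm all reduced by 6 IU at a late review, although the protocol expects basal doses to be stable after about 6 weeks.

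Four stronger readings are tempting and not supported:
- That the lispro arm has no rule at all. SAP 11.3.4 supplies a default.
- That the offset favours albiglutide or inflates the type I error. Upward changes at Week 26 in the lispro arm would favour albiglutide and downward changes would work against it. The documents do not say which will prevail.
- That the arms are 17 days apart. That figure, (183 + 7) − (176 − 3), takes opposite extremes of the visit windows. A comparison of means depends on average timing, nominally 7 days.
- That the lispro-arm injection count is affected too. It is fixed at 21 lispro injections per week whatever the time point.

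**Conclusion.** The mismatch is real and worth correcting because correction is cheap. The albiglutide-arm rule is explicit. The lispro-arm time point is inferred from SAP 11.3.4 and the visit list in 8.1.2.4. The gap of one review assumes that the Surveillance page works the same way at both contacts.

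The effect is probably small: 0 to 1.8 IU/day in the lispro-arm mean under the assumed shares and step sizes, direction unknown. A reader might infer that the test result is in doubt. Even in the stacked case, power stays above 0.97 for a true difference of 15 IU or more. The decision is exposed only if the true difference is near 10 IU or less and the shift runs against it. The gain from the change is an estimate and interval free of an arm-specific timing component.

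The dose endpoint is confirmatory under either version of SAP 11.10, but as that appendix stands the confirmatory test order is not uniquely defined.

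**What to change.** - In SAP 8.1.2.4, apply the Week 25 prescription as the Week 26 dose in both arms, for total, basal, bolus and IU/kg dose.
- Leave the injection-count rules as they are: the albiglutide-arm definition unchanged, and the lispro arm fixed at 21 lispro injections per week. Deleting the arm restriction from the whole heading would put two conflicting count rules on the lispro arm, so the change should be confined to dose.
- State which Surveillance-page entry is used (dose in force or newly set), the same in both arms.
- List the Week 25 substitution in SAP 2.1.
- Report the Week 26 visit prescription in both arms as a sensitivity analysis.
- Separately, reconcile the SAP 11.10 text list and diagram, including whether the percentage-of-subjects endpoint is in the sequence.

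The cost is a few sentences and one derivation rule. No new data are needed: the Week 25 contact is scheduled for both arms, and SAP 6.8 has prescribed doses captured from Visit 2 onward. The small downside is that the comparator value moves about one week ahead of the Week 26 time point named in the protocol.

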8.1.3. Supportive Secondary Efficacy Endpoints

8.1.3.1. HbA_{1c} Change from Baseline over Time

HbA_{1c} change from Baseline by visit will be analyzed analogous to the primary efficacy endpoint using the same MMRM model (Model 1) in the FA population. The observed HbA_{1c} and change from Baseline HbA_{1c} will be summarized descriptively and presented graphically. The least squares means (and standard errors) of change from Baseline HbA_{1c} will be plotted by treatment group.

8.1.3.2. FPG Change from Baseline at Week 26 and over Time

FPG change from Baseline by visit will be analyzed and summarized similarly to weight change from Baseline using Model 2 with FPG replacing weight in the model (Section 8.1.2.3). The analyses will be performed on FA population and all data will be listed.

Due to administrative error in the Time and Events table in the protocol, fasting plasma glucose (FPG) was not collected at Week 26 and will be imputed with fasting serum glucose (FSG) value. Correlation analyses of FPG and FSG values using data from this trial at earlier visit as data allows will be performed to provide an assessment of the validity of this imputation.

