10. For the Screening assessment, a documented examination within six months of the Screening visit would also be acceptable but only when there was NO clinical change (e.g., decrease in visual acuity/visual field) since the last prior funduscopy. The end of treatment/early withdrawal assessment eye exam should be carried out by the investigator.
11. Height measured and body mass index calculated at Screening only. Weight, blood pressure, and heart rate (pulse); obtain blood pressure and pulse after sitting for at least 5 minutes.
12. All 12-lead ECGs to be performed before measurement of vital signs and collection of blood samples for laboratory testing. Subjects to be semirecumbent for 10 to 15 minutes before obtaining the ECG.
13. See Section 6.3.1 for hypoglycemic events criteria and reporting requirements. Subjects will be asked to report hypoglycemic events that occur between study visits in a diary.
14. Fasting is defined as no food or drink (except water) for at least 8 hours before blood draw.
15. Hematology to include complete blood count with red blood cell indices, white blood cell count differential, and platelet count.
16. Clinical chemistry to include glucose, blood urea nitrogen, creatinine, sodium, potassium, chloride, carbon dioxide, calcium, total protein, albumin, total bilirubin, direct bilirubin, alkaline phosphatase, alanine aminotransferase, aspartate aminotransferase, γ -glutamyltransferase, uric acid, magnesium, and phosphorus. Calculate estimated glomerular

filtration rate using the Modification of Diet in Renal Disease formula.

17. Fasting plasma glucose only.
18. Fasting plasma glucose, creatinine, alanine aminotransferase, total bilirubin, direct bilirubin, γ -glutamyltransferase, and alkaline phosphatase only.
19. Urinalysis to include specific gravity, pH, glucose, ketones, microalbumin, creatinine, blood, leukocyte esterase, and nitrites. (If warranted, a microscopic evaluation will be completed.)
20. Thyroid-stimulating hormone assessment at Screening only. Free T4 (reflex) will be measured if TSH is above upper limit of normal.
21. Blood sample for genetic research can be collected at any time during the study after the genetics informed consent has been obtained and the subject has been randomly assigned to treatment group.
22. Urine pregnancy test for women of childbearing potential only and at any time that pregnancy is suspected.

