5.4. Baseline and Study Day

In general, the baseline value for each variable will be defined as the last measurement collected prior to the first dose of randomized study medication.

Study day will be defined as the number of days from the first dose of randomized study medication. The date when a subject receives the first dose of randomized study medication is defined as Day 1. For events after the first dose date, study day is calculated as the difference in days between the first dose date and the date of interest, plus 1 day. For events that occur before the first dose date, study day is calculated as the difference in days between the first dose date and the date of interest. Thus, the day before first dose date is defined as Day -1.

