12. All 12-lead ECGs to be performed before measurement of vital signs and collection of blood samples for laboratory testing. Subjects to be semirecumbent for 10 to 15 minutes before obtaining the ECG.
13. See Section 6.3.1 for hypoglycemic events criteria and reporting requirements. Subjects will be asked to report hypoglycemic events that occur between study visits in a diary.
14. Fasting is defined as no food or drink (except water) for at least 8 hours before blood draw.
15. Hematology to include complete blood count with red blood cell indices, white blood cell count differential, and platelet count.
16. Clinical chemistry to include glucose, blood urea nitrogen, creatinine, sodium, potassium, chloride, carbon dioxide, calcium, total protein, albumin, total bilirubin, direct bilirubin, alkaline phosphatase, alanine aminotransferase, aspartate aminotransferase, γ -glutamyltransferase, uric acid, magnesium, and phosphorus. Calculate estimated glomerular

filtration rate using the Modification of Diet in Renal Disease formula.

17. Fasting plasma glucose only.
18. Fasting plasma glucose, creatinine, alanine aminotransferase, total bilirubin, direct bilirubin, γ -glutamyltransferase, and alkaline phosphatase only.
19. Urinalysis to include specific gravity, pH, glucose, ketones, microalbumin, creatinine, blood, leukocyte esterase, and nitrites. (If warranted, a microscopic evaluation will be completed.)
20. Thyroid-stimulating hormone assessment at Screening only. Free T4 (reflex) will be measured if TSH is above upper limit of normal.
21. Blood sample for genetic research can be collected at any time during the study after the genetics informed consent has been obtained and the subject has been randomly assigned to treatment group.
22. Urine pregnancy test for women of childbearing potential only and at any time that pregnancy is suspected.
23. If hepatitis C antibody is positive, an RNA polymerase chain reaction should be performed on the same sample to confirm the result.
24. As described in Section 3.1, an optional fasting HbA_{1c} value may be determined using a Metrika kit or other finger-stick procedure to provide an initial guide of subject eligibility for investigators.

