2.66	FA		Analysis of Body Weight Adjusted Prescribed Total Daily Bolus Insulin (Insulin Lispro) Dose (IU/Kg) at Baseline, Week 4, Week 5, Week 10, Week 18 and Week 26		
2.67	FA		Summary Statistics for Prescribed Insulin Dose		
2.68	FA		Summary Statistics for Total Number of Weekly Insulin Injections		
Change from Baseline in Fasting Plasma Glucose					
2.75	FA		Summary Statistics for Fasting Plasma Glucose (mmol/L) by Visit		
2.76	FA		Analysis of Change from Baseline in Fasting Plasma Glucose (mmol/L) by Visit		

Efficacy: Tables					
No.	Population	IDSL / TST ID / Example Shell	Title	Programming Notes	Deliverable [Priority]
2.77	FA		Summary Statistics for Change from Baseline in Fasting Plasma Glucose (mmol/L) by Visit and Baseline Fasting Plasma Tertiles		
2.78	FA		Analysis of Change from Baseline in Fasting Plasma Glucose (mmol/L) at Week 26 by Baseline Fasting Plasma Tertiles		
2.79	FA		Statistical Output for the Analysis of Correlation between Fasting Plasma Glucose (mmol/L) and Fasting Serum Glucose (mmol/L) at Screening Visit		
Subjects Achieving HbA1c Target Response					
2.81	FA		Analysis of Proportion of Subjects Achieving HbA1c < 6.5% Response by Visit		
2.82	FA		Analysis of Proportion of Subjects Achieving HbA1c < 7.0% Response by Visit		
2.83	FA		Analysis of Proportion of Subjects Achieving HbA1c < 7.0% Response without Weight Gain at Week 26		
2.84	FA		Analysis of Proportion of Subjects Achieving HbA1c < 7.0% Response without Severe or Documented Symptomatic Hypoglycemia at Week 26		
2.85	FA		Analysis of Proportion of Subjects Achieving HbA1c < 7.0% Response without Weight Gain and without Severe or Documented Symptomatic Hypoglycemia at Week 26		
2.86	FA		Analysis of Proportion of Subjects Achieving HbA1c < 6.5% Response by Visit, Considering Missing HbA1c Values		
2.87	FA		Analysis of Proportion of Subjects Achieving HbA1c < 7.0% Response by Visit, Considering Missing HbA1c Values		

Efficacy: Tables					
No.	Population	IDSL / TST ID / Example Shell	Title	Programming Notes	Deliverable [Priority]
Subjects Who Meet Prespecified Criteria for Severe, Persistent Hyperglycemia					
2.101	FA		Analysis of Proportion of Subjects Who Meet Prespecified Criteria for Severe, Persistent Hyperglycemia at Week 26		
2.102	FA		Kaplan-Meier Analysis of Time to Meeting Prespecified Criteria for Severe, Persistent Hyperglycemia		
2.103	FA		Summary Statistics for Proportion of Subjects Meeting Prespecified Criteria for Severe, Persistent Hyperglycemia		

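### The Week 26 switch from plasma to serum glucose is checked only by correlation, which cannot show a systematic offset between the two specimens

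*SAP*

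**What the plan says.** SAP 8.1.3.2 reports that, because of an error in the Time and Events table, FPG "was not collected at Week 26 and will be imputed with fasting serum glucose (FSG) value". The substituted value enters the by-visit analysis: "FPG change from Baseline by visit will be analyzed and summarized similarly to weight change from Baseline using Model 2". Week 26 is the only visit for which a substitution is described.

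On validity, the same section says "Correlation analyses of FPG and FSG values using data from this trial at earlier visit as data allows will be performed". The list of displays (SAP 11.14.4) has one table for this, Table 2.79: "Statistical Output for the Analysis of Correlation between Fasting Plasma Glucose (mmol/L) and Fasting Serum Glucose (mmol/L) at Screening Visit". No mean paired difference, limits of agreement or calibration is named.

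On baseline, SAP 5.4 says "the baseline value for each variable will be defined as the last measurement collected prior to the first dose of randomized study medication". It gives no rule on specimen type.

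The schedule (Protocol Table 5, repeated in SAP Appendix 2) uses three footnotes to the chemistry row. Footnote 16 defines the full panel: "Clinical chemistry to include glucose, blood urea nitrogen, creatinine" and further analytes. Footnote 17, at Week -1, reads "Fasting plasma glucose only". Footnote 18, at Weeks 4, 5 and 18, lists fasting plasma glucose with a few safety tests.

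**The concern.** A change from baseline is interpretable when both ends are measured the same way. If serum and plasma glucose differ systematically in this trial's samples, subtracting one from the other adds that difference to the change, and it reads as an effect of treatment or time. The planned check measures linear association. The question that matters for a change score is agreement, and a high correlation does not answer it.

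The results exposed are the within-arm FPG changes, the FPG plots over time (Figures 2.61 to 2.63) and the within-arm FPG changes by baseline FPG tertile (SAP 8.2.5, Tables 2.77 and 2.78).

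**Working it through.** The documents give no figure for the offset or the correlation, so there is nothing to reproduce. The check has two parts: reading the schedule, and algebra with assumed values.

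**Schedule.** Laboratory glucose marked in the chemistry row:

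| Visit | Marked |
|---|---|
| Screening | full panel |
| Week -1 | plasma glucose only |
| Week 0 | full panel |
| Weeks 4 and 5 | plasma glucose plus selected tests |
| Week 10 | full panel |
| Week 18 | plasma glucose plus selected tests |
| Week 26 | full panel |
| Early Withdrawal, Follow-up | full panel |

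The full panel is the only scheduled laboratory glucose at Week 26, so it is presumably the source of FSG. SAP Appendix 2 marks the same panel at Week 0, with an overnight fast at both visits.

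**Which visits mix specimens.** One baseline value is subtracted at every visit.
- If baseline is plasma (for example the Week -1 value), Week 26 is serum minus plasma.
- If baseline is serum (the Week 0 panel), Weeks 4, 5 and 18 are plasma minus serum.
- In both cases baseline drops out of the step from Week 18 to Week 26, which is serum at Week 26 minus plasma at Week 18.

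**Algebra.** Let serum = plasma + a.
- Correlation: corr(P, P + a + error) does not depend on a.
- Week 26 change with a plasma baseline: (P26 + a) - P0 = true change + a.
- Weeks 4, 5 and 18 with a serum baseline: P - (P0 + a) = true change - a.
- Serum minus serum: (P26 + a) - (P0 + a) = true change.
- Arm difference at Week 26: a is in both arms and cancels.

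**Numbers (all assumed).** FPG mean 8.5 and SD 2.5 mmol/L, assay noise SD 0.3 in each specimen, true Week 26 changes of -0.70 (albiglutide) and -1.00 (lispro), plasma baseline. For a constant offset, r = 2.5² / (2.5² + 0.3²) = 6.25 / 6.34 = 0.986. The concordance coefficient, which does register an offset, is 12.5 / (12.68 + a²). A simulation with 400,000 subjects per arm gave:

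| Offset (mmol/L) | r | Concordance | Serum minus plasma, two arms | Serum minus serum, two arms | Arm difference |
|---|---|---|---|---|---|
| 0 | 0.986 | 0.986 | -0.70, -1.00 | -0.70, -1.00 | 0.304 |
| -0.2 | 0.986 | 0.983 | -0.90, -1.20 | -0.70, -1.00 | 0.304 |
| -0.5 | 0.986 | 0.967 | -1.20, -1.50 | -0.70, -1.00 | 0.304 |
| -1.0 | 0.986 | 0.914 | -1.70, -2.00 | -0.70, -1.00 | 0.304 |
| +0.5 | 0.986 | 0.967 | -0.20, -0.50 | -0.70, -1.00 | 0.304 |
| serum = 0.95 × plasma | 0.985 | 0.969 | -1.09, -1.38 | -0.66, -0.95 | 0.289 |

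The true arm difference is 0.30; the extra 0.004 is simulation error. The arm difference is the same for the mixed and the serum-to-serum change. It moves only when the offset depends on glucose level: 0.95 × 0.30 = 0.285, a loss of 0.015. Serum minus serum removes a constant offset completely, but under a proportional one it is still scaled by 0.95.

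**The case against.** The substitution is disclosed openly, and the comparison the trial makes is between arms. Model 2 contains visit and treatment-by-visit terms, so a constant offset common to both arms at Week 26 is absorbed by the visit effect. FPG change is a supportive secondary endpoint, and the SAP treats tests outside its hierarchy as exploratory (5.1 and Appendix 10). All of this stands, and it limits the point to within-arm and over-time description.

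Several stronger readings are tempting, and the documents do not support them:
- A reader might infer that baseline is definitely plasma. The SAP never says so. Protocol 6.1 lists FPG as a critical baseline assessment, but Table 5 carries no separate plasma mark at Week 0.
- A reader might take it as settled that a Week 0 serum value exists. Footnote 16 says only glucose, so serum is an inference from the Week 26 substitution.
- A reader might think every FPG-tertile analysis is affected. HbA1c by baseline FPG tertile (SAP 8.2.4) uses FPG only at baseline to form groups, and the Week 26 swap cannot touch it.
- A reader might say the check is bound to pass. No pass rule is stated, and the table shells are in a separate document. What can be said is that no agreement statistic is named.

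It is also fair to object that making Week 26 alone serum minus serum inside the by-visit MMRM would put two baselines into one model with a single baseline covariate. That objection is right, and the fix below avoids it.

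**Conclusion.** The point holds for the within-arm FPG changes, the FPG plots and FPG change by baseline FPG tertile. Any constant offset enters the affected visits in full, and the planned correlation cannot reveal it. Which visits are affected depends on the unstated baseline specimen, but the Week 18 to Week 26 step is affected in either case.

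The size is unknown because the documents give no offset. Over the assumed range of -1.0 to +0.5 mmol/L the within-arm error equals the offset, and the correlation stays at 0.986. The Week 26 arm difference is unchanged by a constant offset and nearly unchanged by a 5% proportional one. Neither the primary conclusion nor the testing hierarchy is at risk. The conclusion assumes that samples followed the schedule and that the Week 26 FSG comes from the chemistry panel. It is worth correcting because the remedy is nearly free.

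**What to change.** 1. In Table 2.79, beside the correlation, report the mean paired FPG-FSG difference with its 95% CI, the limits of agreement and the slope, at every visit with paired values. Confirm first that pairs exist at Screening, where the schedule has no separate plasma mark.
2. Add a separate, named Week 26 analysis of FSG change from Week 0 to Week 26, outside the by-visit FPG MMRM. If Week 0 serum is not available, calibrate FSG to FPG by a regression fitted on the paired samples.
3. State in SAP 8.1.3.2 the specimen used at each visit, including baseline and Week 10. Week 10 and Early Withdrawal also have the panel without a plasma mark, yet only Week 26 is addressed.

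The cost is SAP wording and minor programming on data already collected. No new sample is needed.
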